Each individual enrolled will participate in the study for approximately 3 months. We anticipate enrollment of study subjects will take approximately 15 months. We hope to complete all analyses 2 two years.

STUDY ENDPOINTS:

The primary study endpoints are we have enough patients enrolled to compare VAD-care SBML training and usual training groups.

PROCEDURES INVOLVED:

Approximately 60 advanced HF patients undergo VAD implantation at NMH yearly. During our 15-month study period, up to 75 participating patients and 75 caregivers will be eligible to receive either the SBML VAD self-management curriculum or usual VAD training. Eligible patients will be about to undergo VAD implantation at NMH, age >18, and English-speaking. Eligible caregivers will be identified by a VAD implantation patient, age >18, and English-speaking. Advanced HF patients who are scheduled for VAD implantation will receive information about the study at their pre-implantation clinic visits or during hospitalization. Consenting patients will be asked to provide the name and contact information of their primary caregiver; we will contact the caregivers to explain the study and assess their interest. Patients and caregivers must both agree to participate in the study to be enrolled. All Patient and caregiver VAD self-management training begins before implantation and continues up to the hospitalization for VAD placement.

Study randomization will be conducted via random number generator. After randomization, demographic data including age, sex, race/ethnicity, and socioeconomic (SES) factors such as zip code, highest level of education, and employment status will be collected from patients and caregivers.

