We will estimate checklist score inter-rater reliability using the Kappa (κ) coefficient^{84,87}. Our prior work shows the difference between traditional training and SBML interventions is approximately 33%; traditionally trained simulated skill checklist performance averages 61.47% (SD=24.48) items correct while SBML training performance averages 94.88% (SD=6.63).^{9,48,51,53,88} We anticipate the usual training group in our study will perform similarly to the traditionally trained healthcare providers in our prior studies. Sample sizes of 65 in each group (total =130) achieve 82% power to detect at least 10% difference between the usual group and the SBML training group assuming a mean checklist score of 85% in usual group (SD=25) and 95% in the SBML training group (SD=10) with a significance level of 0.05 using a two-sided t-test. As the distribution of % items correct is likely to be non-parametric, adding 15% requires 75 in each group.⁸⁹ Therefore, our study will be overpowered to detect a 33% difference. We will compare checklist scores on actual patient assessments between usual care and SBML-trained groups using the independent t-test or Wilcoxon rank sum test (if data are non-parametric). We will compare age, sex, race/ethnicity, level of education, employment status, zip code, type of VAD, and VAD indication (DT vs. BTT) between groups using either Chi Square test or independent t-tests. If there is a difference between the randomized groups in any of these variables at the level of $p \leq 0.1$, we will use multiple linear regression or multiple quantile regression (for non-parametric data) to assess these variables independently on scores between the two groups. We will measure skills decay between groups using an analysis of variance (ANOVA) or a non-parametric analysis of variance at 0, 1 and 3-month assessments. Questionnaire results will be compared between groups using Chi-Square, independent t-test, or Wilcoxon rank sum where appropriate.

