The research settings for recruitment and enrollment of patients is Northwestern Memorial Hospital, Northwestern University, Chicago, IL. Patients will be recruited either at the medical center (while the patient is hospitalized) or during a clinic visit. The co-investigators, who provide care to patients with ventricular assist devices (VADs) will share information about the study with patients. If the patient's caregiver is not present at this time, we will contact them via phone or via mailed brochure to explain the study and then consent in person when they arrive for their VAD training.

The PI, CO-I or VAD nurse, will further explain the study to patients and caregivers, encourage them to ask questions, and obtain written informed consent. Patients and caregivers will be informed that if they decline to participate in the study, it will not prejudice current patient care, and they may discontinue participation at any time during the study with no adverse impact to their treatment or care. Verbal and written information provided to potential participants during informed consent will include the following: the purpose of the study, the nature of the questions asked during interviews, the method and frequency of skills assessment completion, the length of time required, the voluntary nature of participation in the study, the ability to not respond or participate in any parts if requested, the freedom to withdraw from the study at any time without consequences, the potential risks and benefits of study participation,

and the confidentiality of information gathered. A brochure with an overview of the study will also be provided. Patients will also be shown their study results, if desired. Patients who are enrolled in INTERMACS will also be informed that INTERMACS will securely transmit data to Northwestern, as well, which is already done for other studies. We will also incorporate language into their consent form that includes a statement about INTERMACS protected health information being transmitted securely to Northwestern. Patients who agree to participate in the study will sign an informed consent form. A copy of the signed consent form will be given to the patient, a second copy of the consent form will be placed in the patient's medical record, and the original copy will be kept and filed by the RC

NUMBER OF LOCAL PARTICIPANTS:

We expect to recruit 75 patients and 75 caregivers. One caregiver will be identified by each patient subject.

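### Randomization states no blocks, strata, ratio or unit; blocking patient-caregiver pairs, stratified by VAD indication, would cheaply protect against an unlucky split

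*Combined protocol and SAP*

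**What the plan says.** Under Procedures Involved, allocation has one sentence: "Study randomization will be conducted via random number generator". In the text supplied, nothing states the ratio, the unit, blocking, stratification or who holds the list. The same section says that "up to 75 participating patients and 75 caregivers will be eligible to receive either the SBML VAD self-management curriculum or usual VAD training", and that "Patients and caregivers must both agree to participate in the study to be enrolled". Number of Local Participants adds: "One caregiver will be identified by each patient subject". That makes up to 75 pairs. Demographics come later: "After randomization, demographic data including age, sex, race/ethnicity, and socioeconomic (SES) factors" and related items are collected once the arm has been assigned.

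Data and Specimen Management gives the sample size: "Sample sizes of 65 in each group (total =130) achieve 82% power to detect at least 10% difference". The inputs behind that figure are stated as "assuming a mean checklist score of 85% in usual group (SD=25) and 95% in the SBML training group (SD=10". The test named there is a t-test, two-sided at the 5% level. The plan then adds 15% because the scores may not be normal, which gives 75 per group. The main comparison is an independent t-test, with no statement of whether it is pooled or unequal-variance, or a Wilcoxon rank sum test. VAD indication (DT or BTT) is one of eight variables compared between arms after randomization. Regression adjustment follows if any of them differs at p≤0.1.

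**The concern.** The sample size relies on equal arms, and nothing stated about allocation produces them. The assumed SD is 2.5 times as large in the usual arm, so the direction of an uneven split matters. Fewer people in the usual arm means less power. A pooled t-test then also understates the standard error and rejects too often; the opposite split makes it conservative.

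Indication is a variable that the investigators already plan to check, yet it is not balanced by design. Adjusting for it only when a significance screen fires makes the analysis model depend on the data.

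Training cannot be hidden from participants, and they may withdraw at any time. A pair that leaves on learning its arm might therefore do so before the demographic form is completed.

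**Working it through.** **Inputs from the documents.** 75 pairs; means 85 and 95; SDs 25 (usual) and 10 (SBML); two-sided level 0.05; 65 per group raised to 75. The figure of 75 per group (150 in all) matches the 75 patients plus 75 caregivers, so the plan counts people. Steps 2 to 4 do the same and treat them as independent.

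**Assumptions not in the documents.** Unrestricted 1:1 allocation of pairs; a DT share of 30% to 50%.

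**1. The plan's own figure.** At 65 per group the standard error is √(625/65 + 100/65) = 3.340 and the noncentrality is 10/3.340 = 2.994. Noncentral t power is 84.4% (pooled) or 84.1% (Welch), slightly above the stated 82%. A Wilcoxon allowance (65 × 0.955 ≈ 62 per group) gives 82.4% to 83.3%, so 82% may be a rank-test figure. The inflation reproduces: 65 × 1.15 = 74.75, rounded up to 75.

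**2. Arm sizes.** With X ~ Binomial(75, 0.5), the SD is √(75 × 0.25) = 4.33 pairs.
- 43:32 or worse: 2 × P(X ≤ 32) = 24.8%.
- 45:30 or worse: 2 × P(X ≤ 30) = 10.5%.
- 30 or fewer pairs in the usual arm: 5.3%.

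**3. Power for 10 points, Welch.** Standard error = √(625/n_usual + 100/n_SBML), with noncentral t on Satterthwaite degrees of freedom.

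| Usual / SBML people | Standard error | Power |
|---|---|---|
| 75 / 75 | 3.109 | 89.0% |
| 60 / 90 | 3.395 | 82.8% |
| 90 / 60 | 2.935 | 92.2% |

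**4. Level of a pooled t-test, equal means, SDs 25 and 10.** Level ≈ 2 × [1 − Φ(1.976 × pooled SE / true SE)].
- 60/90: pooled variance (59 × 625 + 89 × 100)/148 = 309.3; pooled SE 2.931; true SE 3.395; level 8.8%.
- 90/60: pooled variance 415.7; pooled SE 3.398; true SE 2.935; level 2.2%.
- 75/75: the two SEs agree; level 4.8%, or about 5%.

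Simulation at the slightly more extreme splits of 58/92 and 92/58 gives 9.8% and 2.1%. Welch stays at about 5% at every split tried.

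**5. Averaged over all splits.** Weighting by the binomial probabilities gives mean Welch power of 88.5% against 89.0% when even, a loss of about half a point. The mean pooled level is 5.0% by the formula and 5.3% by simulation.

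**6. Indication.** In simulated trials of 75 pairs, the DT share differs between arms by 20 points or more in 6% of trials (30% DT) to 9% (50% DT), and by 10 points or more in 35% to 38%.

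**The case against.** The strongest reply is that this is a design preference and a reporting gap. Much of it stands.

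- **Power.** A reader might infer that the stated power holds only for near-equal arms. The documents do not support that. The 60/90 case, at 82.8%, still exceeds 82%. On this basis power falls below 82% only with 29 or fewer usual-arm pairs (58/92 gives 81.7%), which has probability 3.2%. The opposite imbalance raises power.
- **Level.** A reader might also infer that the 5% level fails generally. The 8.8% needs a pooled test, which the plan does not specify, and SDs of 25 and 10 under equal means. The plan attaches those SDs to different means. If training changed nothing, the arms would share one SD and the pooled test would hold its level at any split. Welch alone removes the problem without blocking. The Wilcoxon fallback does not fully protect: with equal means and these SDs, simulation at one score per pair gives 8.7% at 29 usual v 46 SBML.
- **Scheme.** Simple randomization is an inference. A random number generator can also produce a blocked list; the text is silent.
- **Indication.** It is screened and adjusted for, so chance imbalance would not go unaddressed. Stratifying on one of eight variables barely quiets the screen: if the tests were independent, the chance of at least one trigger falls from 1 − 0.9⁸ = 57% to 1 − 0.9⁷ = 52%.
- **Baseline data.** Patient socio-demographic data, VAD type and indication also come from INTERMACS, so the exposure is mainly caregiver data. The documents do not show that any pair leaves after allocation.
- **Unit of analysis.** This moves power far more. One score per pair, at 37/38, gives about 60% even with perfect blocking. That is a separate matter.

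What survives is that a trial is run once and analysed at the split it gets, and better methods than those stated cost almost nothing.

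**Conclusion.** The point holds as a cheap improvement. No restriction on allocation is stated, although the sample size presumes equal arms with very different SDs. Under unrestricted allocation, about 1 trial in 19 (5.3%) would put 30 or fewer pairs in the usual arm. At 30 pairs, power would be about 6 points below an even split, and a pooled t-test could run at nearly 9%. In expectation the cost is negligible, so the benefit is protection against an unlucky split; the plan's power and error rate are not generally wrong.

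The power and level figures rest on unrestricted 1:1 allocation of pairs, people treated as independent, and the plan's SDs; the level figure also needs those SDs under equal means and a pooled test. The indication figures depend on a DT share that the documents do not give.

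**What to change.** **Procedures Involved.** State that patient-caregiver pairs are randomized 1:1 in permuted blocks of randomly varying size (for example 4 and 6), stratified by VAD indication, from a list held by someone who does not recruit, train or score. With those block sizes an unfinished block can leave a stratum at most 3 pairs out of balance, so two strata differ by at most 6 pairs overall, against 15 at 45:30. Complete the demographic forms before allocation; this matters mainly for caregivers.

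**Data and Specimen Management.** Name an unequal-variance (Welch) test or robust standard errors. Include the indication stratum in the Aim 1 and Aim 2 models whatever the p≤0.1 screen shows.

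**Cost.** A new computer-generated list, a short protocol edit and an earlier form. The small downside is some predictability of allocation in a single-centre trial where trainers and participants know the arm. Random block sizes and an independent list holder limit it.

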Two VAD nurses will perform usual training only, which is the current standard of care. First, patients and caregivers watch a video produced by the VAD manufacturer. Subsequently, the VAD nurse trains the patient and caregiver per usual routine with a non-implanted VAD. These meetings occur 1 to 3 times depending upon patient and caregiver availability and are not standardized. During the VAD implantation hospitalization, the caregiver completes a written examination to assess knowledge. The VAD nurse observes patient and caregiver completion of skills and deems competence based only on observation. Historically, patient and caregivers are variably able to participate in training sessions. If the patient is too ill to participate in training before VAD implantation, only the caregiver completes training and the patient is trained during the hospital stay for implantation at which point they are significantly clinically improved.

Three VAD nurses will administer SBML training. The SBML training group will first 1) watch the VAD video, then 2) participate in pre-intervention assessments using the simulator for a) driveline exit site sterile dressing changes; b) performing controller self-tests; c) changing power sources; d) troubleshooting emergent VAD-related malfunction; and e) recognizing specific signs and symptoms requiring immediate contact with the VAD team. The patient and caregiver

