then will participate in deliberate practice on the simulator with feedback from the instructor. We anticipate 2 training sessions of 1-2 hours each to become proficient in these skills. After training, the patient and caregiver complete a post-intervention assessment on the simulator using the checklists. At the end of training, the patient and caregiver will complete the written examination to assess knowledge and will be required to meet or exceed the MPS on the checklists and written examination. If they fail to meet the MPS, they will receive additional training until they meet the MPS. If the patient is ever too ill, only the caregiver will participate in the training and the patient will be trained during the hospital stay for implantation. Both training groups. After training, we will ask participants to rate their educational experience and their confidence in performing each of the 5 VAD self-management tasks [via a questionnaire adapted from our previous work. All participants will demonstrate the five skill domains on the actual VAD patient during the implantation hospitalization (Time 0), and at one and three months after training to assess skill retention. Assessments will be performed during office visits, as patients are seen at least monthly after VAD implantation, or re-hospitalizations. If caregivers cannot attend, assessments will be performed via internet video. We anticipate the majority of enrolled patients will have internet access; alternatively, we will arrange sessions at their local library.

A trained VAD nurse (who is not assigned to teach the curriculum) will perform all patient and caregiver assessments using the checklist. In the absence of this nurse, the PI or a Co-I will perform assessments; we expect this to be rare. The trained VAD nurse, the PI and COCo-I will be blind to the intervention received by the patient and caregiver. A random sample of 25% of all assessments will be double scored by both the VAD nurse and PI or Co-I to assess inter-rater reliability.

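### The rule giving the blinded nurse every checklist assessment can be read to include the SBML-only simulator post-test, and the PI's simulation-training role conflicts with blind scoring on any reading

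*Combined protocol and SAP*

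**What the plan says.** All of this is in the combined protocol and SAP, under Procedures Involved unless stated.

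- **SBML arm.** Participants watch the video, then "participate in pre-intervention assessments using the simulator". They practise with an instructor, and afterwards "the patient and caregiver complete a post-intervention assessment on the simulator using the checklists". Anyone below the required standard (MPS) is trained further until it is met. Three VAD nurses administer this training. No scorer is named for either simulator test.
- **Usual-training arm.** No simulator or checklist test is described before Time 0. The VAD nurse watches the skills and "deems competence based only on observation".
- **Both arms.** "All participants will demonstrate the five skill domains on the actual VAD patient during the implantation hospitalization (Time 0"), and again at one and three months.
- **Who scores.** "A trained VAD nurse (who is not assigned to teach the curriculum") "will perform all patient and caregiver assessments using the checklist". The PI or a Co-I steps in when she is absent, and 25% of all assessments are double scored by the nurse and the PI or a Co-I.
- **Blinding.** The nurse, the PI and the Co-I "will be blind to the intervention received by the patient and caregiver". No means of keeping the blind is given.
- **Primary outcome** (Data and Specimen Management). On-patient checklist scores and written examination scores, compared between arms.
- **PI duties** (Resources Available). The PI's listed responsibilities include simulation training.

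**The concern.** The on-patient checklist is scored by an observer, and it is the measure on which the study is powered. Its credibility rests on the scorer not knowing the arm. A simulator post-test takes place only in the SBML arm, so scoring one reveals the allocation. If the same person then scores Time 0 and the two retention visits, any leniency or severity tied to that knowledge goes straight into the between-arm difference.

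Double scoring would not expose this. Two raters who both know the arm can agree closely and share the same lean, so a high kappa gives no reassurance about it.

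**Working it through.** **Step 1. List each assessment against the scoring rule.**

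| Assessment | Arm | Checklist named? | Scorer named? | Reveals arm to its scorer? |
|---|---|---|---|---|
| Simulator pre-test | SBML only | No | No | Yes |
| Simulator post-test | SBML only | Yes | No | Yes |
| On-patient, Time 0, one and three months | Both | Yes (under Data and Specimen Management) | Yes, if the rule refers to these | Not in itself |

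**Step 2. Literal reading.** The rule covers every assessment made with the checklist. The post-test is expressly one of these. Its scorer is then the blinded nurse or a blinded back-up, and that person knows the arm before Time 0. The rule and the blinding statement cannot both be met. The pre-test adds to this only by inference, because the text does not say that it uses the checklist.

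**Step 3. Narrow reading.** The rule covers only Time 0, one and three months. The nurse's blind can then hold. Two gaps remain:
- nobody is assigned to score the simulator tests or to decide whether the MPS is met;
- nothing keeps the outcome nurse, the PI or a Co-I out of simulator sessions or away from their checklists.

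**Step 4. The PI, on either reading.** One section makes the PI responsible for simulation training. Another makes the PI a blind back-up scorer and one of the possible second scorers for the 25% sample. As those duties are written, they conflict.

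**Step 5. Illustrative size.** The plan has no figure for scoring bias to reproduce. The inputs from its sample-size paragraph are SD 25 (usual), SD 10 (SBML), 65 per group and a two-sided 5% test. Observations are taken as independent, as in the plan's own calculation.

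SE of the difference = √(25²/65 + 10²/65) = √(725/65) = √11.15 = 3.34 points.

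With no true effect and a lean of *b* points towards SBML, the rejection rate is P(Z > 1.96 − b/SE) + P(Z < −1.96 − b/SE).

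| Assumed lean b (points) | b/SE | Rejection rate |
|---|---|---|
| 0 | 0 | 0.050 |
| 1 | 0.30 | 0.048 + 0.012 = 0.060 |
| 2 | 0.60 | 0.087 + 0.005 = 0.092 |
| 3 | 0.90 | 0.144 + 0.002 = 0.146 |
| 5 | 1.50 | 0.322 + 0.000 = 0.322 |

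A 2-point lean would also add 2 points to a planned difference of 10.

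**The case against.** The best defence is context. Just before the scoring rule the text turns from arm-specific training to procedures common to both groups. It describes the on-patient demonstrations and then uses the word assessments for office visits and re-hospitalizations. The rule follows directly, so its scope may well be those visits only. The simulator tests sit inside the programme that the three SBML nurses administer, and the scoring nurse is defined as someone who does not teach. On that reading the SBML nurses score the simulator tests, and for the nurse there is no contradiction.

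This defence has force, and it rules out the stronger inference a reader might draw: that the plan instructs the nurse to score the simulator tests, at least twice per SBML participant, so that unblinding is complete. The documents do not support that, for four reasons:
- the plan never expressly gives her the simulator tests;
- only the post-test is said to use the checklists;
- a back-up may score either occasion, so the simulator scorer and the Time 0 scorer can be different people;
- part of the primary outcome is a written examination, which is not a checklist rating.

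The defence does not settle the matter. The rule has no limiting words, although the analysis text does specify on-patient scores when it means them. Before the rule, the only assessment described as using the checklists is the simulator post-test. The SBML nurses' role as simulator scorers is implied and never stated. The argument also leaves the PI's two roles untouched. One could suppose that responsibility for simulation training means oversight without contact with trainees, but the plan does not say so.

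**Conclusion.** The point holds as an unresolved conflict in the plan, not as a demonstrated loss of blinding. The literal rule defeats the blind for the checklist part of the primary outcome. The narrow rule preserves the nurse's blind but leaves the simulator scorer unassigned. On both, the PI as described cannot be a blind back-up or second scorer. Whether a given Co-I has the same problem cannot be judged from the text available.

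The effect on the result is not known. Over assumed leans of 1 to 5 points, the false-positive rate would run from about 6% to 32%, and a lean of 2 points gives about 9%. These figures show how sensitive the test is if scorers know the arm. They do not show that they would know it, or that they would lean. The documents give no basis for choosing a value.

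The ambiguity should be removed before assessments begin, because a broken blind cannot be repaired in the analysis.

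**What to change.** Replace the scoring sentence with wording to this effect:

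*A trained VAD nurse who teaches neither arm performs all on-patient assessments at Time 0, one and three months. The SBML instructors score the simulator pre-tests and post-tests and decide whether the MPS is met. The outcome nurse, and every back-up or second scorer, takes no part in simulator sessions and does not see the simulator checklists. Only a PI or Co-I with no involvement in simulation training may act as back-up or second scorer.*

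State also that the 25% double-scored sample is drawn from the on-patient assessments.

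**Cost.** This is a change of wording. Instructors already attend the simulator sessions to give feedback, so no post is added. The PI must either give up outcome scoring or have no part in simulation training. The real downside is that simulator scores and MPS decisions come from unblinded instructors certifying their own trainees. That is tolerable because the plan states no between-arm use for those scores.

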After VAD implant, patients are managed by the VAD team with frequent office visits. Complications and re-hospitalizations are documented in outpatient and/or inpatient medical records. Patients admitted to a local hospital are typically transferred to NMH for care. If patient is admitted to another hospital, they are customarily transferred to NMH to manage the VAD. We believe we will be able to capture all data about driveline infections and re-hospitalizations prospectively.

NMH's infection prevention department also tracks *all* VAD related driveline infections using definitions in the INTERMACS database.³⁷ We will assess patient factors at time of infection and during re-hospitalization to evaluate differences between the SBML and usual VAD training groups such as age, sex, body mass index, and the Charlson comorbidity codes. The Charlson score is based on 19 chronic disease comorbidities derived from the International Classification of Disease Revision 9 (ICD-9) codes and predicts one-year mortality for hospitalized patients. We can obtain all admission ICD-9 codes from our Enterprise Data Warehouse⁹³ which also convert ICD-10 codes to their corresponding ICD-9. We will obtain additional data using the INTERMACS database (includes all NMH patients), which provides type of VAD, VAD indication (DT vs. BTT), and infection and re-hospitalization rates.

DATA AND SPECIMEN MANAGEMENT:

Primary outcome measures are comparisons of VAD-care checklist assessments on the patient and written examination scores between SBML and usual training groups. Secondary outcome measures include self-management skill decay in the five domains from 0 to 3 months and comparisons of post-training questionnaires between groups.

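### The written exam is a primary outcome, but it is described differently in the two arms, and the plan does not say whose score, which attempt or which sitting is compared

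*Combined protocol and SAP*

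**What the plan says.** The protocol, under Data and Specimen Management, names two primary outcome measures: "Primary outcome measures are comparisons of VAD-care checklist assessments on the patient and written examination scores between SBML and usual training groups". It gives no role, attempt or time point for the exam.

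Procedures Involved describes the exam separately for each arm.

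- **Usual training:** "During the VAD implantation hospitalization, the caregiver completes a written examination to assess knowledge". A patient exam is not mentioned and no exam pass mark is stated. The next sentence concerns skills, not the exam: "The VAD nurse observes patient and caregiver completion of skills and deems competence based only on observation".
- **SBML:** "the patient and caregiver will complete the written examination to assess knowledge and will be required to meet or exceed the MPS". This sitting comes once training has finished, and the standard covers the checklists as well as the exam. The repeat rule follows: "If they fail to meet the MPS, they will receive additional training until they meet the MPS".

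The same section then lists what both groups do: a post-training questionnaire, and a demonstration of the five skill domains on the patient at Time 0, one month and three months. The exam is not in that list.

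The analysis text in Data and Specimen Management names tests for checklist scores, skills decay and questionnaires. Its sample size is for the checklist. It does not mention the exam.

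**The concern.** An outcome compared between arms should be measured on the same kind of person, under the same rule, in both arms. As described, the exam differs in three respects.

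1. **Role.** Caregivers only are named in usual training; patients and caregivers are named in SBML.
2. **Pass gate.** SBML members repeat until they pass; no such rule is stated for usual training.
3. **Timing.** The exam falls during the implantation admission in one arm and at the end of training in the other.

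Randomization does not remove these differences, because they arise after allocation. If every collected score were compared, SBML patients and caregivers with a floor at the MPS would be set against ungated usual-arm caregivers. Part of a difference on a named primary outcome could then reflect how the exam was given. With no definition on record, the choice of role and attempt could also be made after scores are seen.

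**Working it through.** **The plan's own figure.** The only stated power is for the checklist: 82% with 65 per group, means 85 (SD 25) and 95 (SD 10), two-sided 0.05. A noncentral-t calculation gives 84.1% (Welch) or 84.4% (pooled), so the stated figure is slightly conservative. It says nothing about the exam, for which the documents give no mean, SD, MPS or failure rate. **Every exam input below is an assumption.**

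**Role mix.** Let P and C be the patient and caregiver mean scores with no training effect. With equal numbers of each in SBML and caregivers only in usual training, the difference is (P + C)/2 − C = (P − C)/2. A gap of 5 points gives 2.5 points. The direction is unknown.

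**Pass gate, total shift.** Assume first-attempt scores have mean μ and SD σ in both arms, and that final SBML scores are analysed. Put a = (MPS − μ)/σ. The first-attempt failure rate is Φ(a).

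- Lower shift (failers end exactly at the MPS): MPS·Φ(a) + μ(1 − Φ(a)) + σφ(a) − μ
- Upper shift (failers end up scoring like first-time passers): σφ(a)/(1 − Φ(a))

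For μ = 80, σ = 10, MPS = 75: a = −0.5, Φ = 0.309, φ = 0.352. Lower: 75 × 0.309 + 80 × 0.691 + 3.52 − 80 = 1.98. Upper: 3.52/0.691 = 5.09.

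**Pass gate, split into real gain and artefact.** Retraining is part of the intervention, so the total shift is not all bias. Let the true score be normal with variance rσ² and the measurement error have variance (1 − r)σ², where r is reliability. Anyone scoring below the MPS has true knowledge raised to at least the MPS and receives a new score that must be a pass. The real gain is the change in mean true score; the artefact is the rest of the observed shift (simulation, 4,000,000 draws).

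| Assumed mean, SD, MPS | Fail first time | Total shift, lower to upper | Observed = real + artefact, r = 0.8 | Artefact, r = 0.9 to 0.6 |
|---|---|---|---|---|
| 90, 8, 75 | 3% | 0.1 to 0.6 | 0.21 = 0.04 + 0.17 | 0.1 to 0.3 |
| 80, 10, 70 | 16% | 0.8 to 2.9 | 1.49 = 0.53 + 0.96 | 0.6 to 1.6 |
| 80, 10, 75 | 31% | 2.0 to 5.1 | 3.19 = 1.49 + 1.70 | 1.1 to 2.7 |
| 80, 10, 80 | 50% | 4.0 to 8.0 | 5.87 = 3.38 + 2.49 | 1.6 to 3.9 |

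**Sensitivity.**

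- A beta distribution on 0 to 100 with the same means and SDs gives failure rates of 5.7%, 16.1%, 28.1% and 44.8%, and total shifts of 0.35 to 1.3, 1.1 to 3.2, 2.2 to 5.0 and 4.0 to 7.3. The real/artefact split was not repeated on a bounded scale.
- If retraining lifts true knowledge to at least MPS + 5, the artefact at r = 0.8 falls to about 0.65, 1.03 and 1.35 for MPS 70, 75 and 80.
- If each retake were an independent draw with no learning, the whole gap would be artefact: 2.8 to 14.8 points for means of 80 to 85, SD 10 and MPS 75 to 90. That is an extreme.

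**Timing.** The mismatch is partial: "All Patient and caregiver VAD self-management training begins before implantation and continues up to the hospitalization for VAD placement". When a patient is too ill beforehand, "the patient will be trained during the hospital stay for implantation". The documents give nothing from which to size its effect.

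**Caregivers only.** 75 caregivers split equally give 37 per arm. With SD 10 the standard error is 10 × √(2/37) = 2.32, and a two-sided t-test at 0.05 has 80% power at 6.60 points. If the exam instead had the checklist's assumed SDs (25 and 10), power for 10 points would be about 60%.

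**The case against.** The strongest reply is that retraining to a standard is the intervention. Background defines mastery learning by variable training time and a uniform result, so a higher score after retraining is partly the effect the trial sets out to show. This stands, and it is why the working separates real gain from artefact. It does not cover the role mix, nor the lift that comes from keeping only passing scores on an imperfect test.

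A second reply is that little depends on the exam. Both Aim 1 hypotheses, the sample size and the named primary test concern skills, and the checklist at Time 0 has a common sitting for all participants. This also stands and limits the stakes.

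A reader might go further and infer any of the following. The documents do not support them.

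- *Usual-arm patients never sit the exam.* The usual-training text is silent about a patient exam; it does not rule one out.
- *A difference on the exam could not be attributed to training at all.* The problem arises only if roles are pooled or final scores are used, and the plan commits to neither. In one plausible case the artefact is a few tenths of a point or less.
- *The remedy must be the Time 0 checklist as sole primary outcome.* Aim 1 also compares arms at one and three months, and change over time, listed as secondary, is not the same comparison.
- *A first exam attempt precedes all MPS retraining.* The MPS also applies to the checklists, and the text does not settle whether checklist retraining can come before the exam.

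**Conclusion.** The point holds as a missing and asymmetric definition of a named primary outcome. The arms' exam descriptions differ in role and pass rule, and partly in timing. The available text fixes neither role, attempt nor sitting, and names no test or sample size for the exam. It should be corrected before exam scores are examined.

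That a bias will occur is not shown, and its size cannot be derived from the documents. For reliability 0.6 to 0.9 and retraining that lifts true knowledge just to the MPS, the pass-gate artefact is 0.1 to 3.9 points across the four assumed cases. It is smaller if retraining achieves more, and larger only if retakes involve little learning. Pooling roles would add half of any patient-caregiver gap. The role and attempt mismatch does not reach the checklist comparison on the patient.

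**What to change.** Define the exam comparison identically in both arms:

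- **Role:** caregivers only, the one role that both arms are stated to examine.
- **Attempt:** the first exam attempt. Describe it as knowledge before any retraining triggered by the exam, and require SBML first-attempt scores to be recorded, since no available section says they are.
- **Test:** name one, for example the t-test or Wilcoxon rank sum test already chosen for the checklist.
- **Timing:** state each arm's sitting and acknowledge the difference.
- **SBML final result after reaching the MPS:** report separately as a process measure.

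Whether the exam stays primary is the sponsor's choice. If it becomes secondary, the checklist comparisons at Time 0, one and three months under Aim 1 should keep their stated status.

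**Cost.** Protocol wording, plus recording first-attempt scores where this is not already done. The comparison leaves out the effect of exam-triggered retraining. It rests on about 37 caregivers per arm (equal allocation assumed), so it has 80% power only for about 6.6 points at an assumed SD of 10. A repeat exam for everyone at Time 0 would align the timing, but SBML members would already have sat it. An assumed 3-point retest advantage, with 37 per arm and SD 10, would give about 25% rejection with no true difference.
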